Appendix A. Nocturia Impact Diary

NOCTURIA IMPACT DIARY[®]

This nocturia (getting up to void at night) diary will assess the daily impact of nocturia on your everyday life. Please answer the questions in the late afternoon or evening and use the scale from 'not at all' to 'a great deal':

Thinking over the day, to what extent....	0) Not at all	1) Slightly	2) Moderately	3) Quite a bit	4) A great deal
1) Was it difficult to concentrate?	0) ____	1) ____	2) ____	3) ____	4) ____
2) Did you feel low in energy and/or tired?	0) ____	1) ____	2) ____	3) ____	4) ____
3) Were you unable to be productive at work or complete your personal, daily activities?	0) ____	1) ____	2) ____	3) ____	4) ____
4) Did you avoid participating in activities that you enjoy?	0) ____	1) ____	2) ____	3) ____	4) ____
5) Did you feel irritable or moody?	0) ____	1) ____	2) ____	3) ____	4) ____
6) Did you limit your fluid intake?	0) ____	1) ____	2) ____	3) ____	4) ____
Thinking about last night, to what extent	0) Not at all	1) Slightly	2) Moderately	3) Quite a bit	4) A great deal
7) Did you lie awake without being able to return to sleep after getting up to use the bathroom at night?	0) ____	1) ____	2) ____	3) ____	4) ____
8) Were you worried about tripping or falling?	0) ____	1) ____	2) ____	3) ____	4) ____
9) Did you feel you got too little sleep?	0) ____	1) ____	2) ____	3) ____	4) ____
Overall, to what extent...	0) Not at all	1) Slightly	2) Moderately	3) Quite a bit	4) A great deal
10) Do you worry that the nocturia will get worse in the future?	0) ____	1) ____	2) ____	3) ____	4) ____
11) Are you concerned with where the bathroom is when away from home overnight?	0) ____	1) ____	2) ____	3) ____	4) ____
12) Does nocturia presently impact your life?	0) ____	1) ____	2) ____	3) ____	4) ____

Nocturia Impact Diary[®] is protected by international copyright / copyright registration, with all rights reserved to Ferring Pharmaceuticals A/S. Do not use without permission. For information on, or permission to use Nocturia Impact Diary[®], please contact MAR Research Trust.

Appendix B. Nocturnal Voids

Voiding diary

1. Do you have any voiding event to report?
 YES
 NO
2. When did the voiding event take place?
----- (format in HH:MM AM/PM)

Appendix C. Case Report Form

Available upon request.

Appendix D. Discussion Guide

SUBJECT DISCUSSION GUIDE

Subject interviews about the impact of nocturia on a subject's health related quality of life and deriving a meaningful change threshold on the Nocturia Impact Diary (NI Diary) and number of nocturnal voids

Interview date: _____ / _____ / _____
MM DD YYYY

Location of interview: _____, _____
City State

Name of interviewer: _____

1 Objectives

The objectives for this study are to explore the impact of nocturia on a subject's health related quality of life (HRQOL). Furthermore, the study aims to assess what a meaningful change is on the Nocturia Impact Diary ([Appendix A](#)) and for the number of nocturnal voids.

The interview is divided into the following sections:

- Introduction to the study (5 minutes)
- Part 1: Experience of living with nocturia and its impact on sleep and HRQOL (15 minutes)
- Part 2: Discussion about the NI Diary and meaningful change (25 minutes)
- Part 3: Discussion about nocturnal voiding frequency and what reduction would be meaningful (10 mins)
- Part 4: Rating of change on the patient global assessment of change and patient global impression of severity (5 minutes).

Using the schedule above, the interview should take no more than **1 hour**.

2 Introduction

2.1 Prior to the Interview

Interviewer to review the purpose of the study and confidentiality arrangements, and ask subject's permission to audio record the interview.

- Introduce yourself and state that you work for a research company called Clinical Outcomes Solutions that works closely with pharmaceutical companies to assess how health conditions and treatments impact people's lives.
- Thank the subject for agreeing to participate in the telephone interview.

2.2 Explanation of the Study:

Interviewer to state:

- *The aim of this interview is to find out about your experiences of needing to go to the bathroom at night and how this impacts you. This condition is often referred to as 'nocturia', are you okay with us using the term 'nocturia'?*
 - If the subject is not okay with this, refer to "the need to go to the bathroom at night to urinate" or the subject's preferred reference term.
- *In the first part of the interview I'd like to understand how nocturia affects you and what it is about nocturia that you'd like to see change or improve, for example after taking treatment.*
- *I'll also ask you some specific questions about how often you go to the bathroom at night to urinate and again, I'd like to understand what kind of improvement you'd like to have in terms of how often you go to the bathroom at night.*
- *In the next part of the interview, I'll ask you to look at a short diary questionnaire and talk about how you might respond to the diary to reflect your experiences.*
- *Finally, at the end of the interview I'm going to ask you two other questions. These two questions ask about whether your symptoms have changed and how bad/good they are at the moment.*
- *All of this should take us no longer than 1 hour.*
- *I'll explain all of this again, as we go through the interview but is there anything so far that you have questions about?*
- *Okay, so just to explain, I'm going to audio record the interview to enable me to pay careful attention to what you say and to make certain we accurately capture the information that you provide to me during the interview.*
- *The audio recording will not be shared with the sponsor (ie, the pharmaceutical company). However, a written version of this interview will be prepared that removes any information that would identify you personally.*
- *Please try to speak clearly so that your comments can be heard.*

- *Please don't be afraid to voice any of your opinions. There are no right or wrong answers. If anything isn't clear, please tell me and I will try to explain better, okay?*
- *You may stop the interview at any point you feel the need to, and you may decline to answer any question if you don't feel comfortable.*

Reassure the subject about confidentiality:

- *Your name and contact information will remain with Clinical Outcomes Solutions and will only be accessible to staff members directly involved with this project.*
- *Any information you provide will be reported in a way that protects your privacy by avoiding any mention of your name or other information that could identify you.*
- *The word for word transcript of this interview will be shared with the sponsor of this study (ie, the pharmaceutical company), but your name or any information that identifies you will be removed first.*

2.3 Final Steps

Ask the subject if they have any questions.

Start recording the interview and ask: Do you agree to have this interview audio recorded? Are you ready to begin?

2.4 Important Notes to the Interviewer

Do not lead the subject, we want their open responses. Do probe where appropriate. Cover all the main parts of the interview guide, it is not critical that it flows in the order given, especially if something comes up earlier on in your discussions.

Any medical questions that a subject may raise just explain that you are not a medical professional and that she/he should speak to a physician.

Allow subjects enough time to answer the questions, especially as this is a telephone interview and you cannot observe any non-verbal cues.

3 Discussion Topics

NB: Please remember to allow subjects to respond spontaneously to the following questions, however, do encourage the subject to talk more about the issues that they raise. Probes have been included to help with this but only use when a Subject has not spontaneously mentioned the relevant issue(s).

Some key probes that you can use:

- Tell me more about that?
- How does it make you feel?
- Can you talk more about?
- Is it always like this?

Part 1: Experience of living with nocturia and its impact (15 minutes)

Introduction by interviewer: *So in this first part of the interview I'd like to start by asking you about your nocturia and how it impacts your day-to-day life. In particular, I'd like to ask you about how your nocturia affects you now, now that you have completed the clinical trial you have just been part of, and then I'd like you to think back to the time before the clinical trial and tell me how your nocturia affected you then. After that, I'm going to ask you to tell me about any change you may have experienced over the clinical trial.*

Firstly, how long is it since you finished the trial?

1. **Okay thinking about now that you have completed the clinical trial you have just been part of, can you tell me about how your nocturia is, now?**

[Try to focus the subject on discussing the symptoms of nocturia, rather than its impact].

- a. What is it like?
- b. What physical things do you experience?
- c. Thinking about a typical night now (*having completed the trial*), how many times do you typically get up in the night to urinate?

2. **Can you tell me about how your nocturia impacts your life now?**

[Encourage the subject to spontaneously mention the different ways nocturia impacts them. If any of the areas below are not mentioned, then probe specifically on these].

- a. Too little sleep?
- b. Problems with falling back to sleep?
- c. Tiredness?
- d. Ability to concentrate?

- e. Productivity at work
- f. Performing daily activities?
- g. Avoidance of activities that you enjoy?
- h. Mood?
- i. Worry about tripping or falling?
- j. Worry about finding a toilet when away from home?
- k. Worry about waking others up in the house?
- l. Worry about worsening of symptoms?
- m. Limited fluid intake?

3. Now thinking back to the time before the clinical trial you have just completed, can you tell me about your nocturia as it was then?

[Try to focus the subject on discussing the symptoms of nocturia, rather than its impact].

- a. What was it like then?
- b. What physical things did you experience?
- c. Thinking about a typical night then (*before the trial*), how many times did you typically get up in the night to urinate?

4. Can you tell me about how your nocturia impacted your life before the clinical trial?

[Encourage the subject to spontaneously mention the different ways nocturia has impacted them. If any of the areas below are not mentioned, then probe specifically on these].

- a. Too little sleep?
- b. Problems with falling back to sleep?
- c. Tiredness?
- d. Ability to concentrate?
- e. Productivity at work
- f. Daily activities?
- g. Avoidance of activities that you enjoy?
- h. Mood?
- i. Worry about tripping or falling?
- j. Worry about finding a toilet when away from home?
- k. Worry about waking others up in the house?
- l. Worry about worsening of symptoms?
- m. Limited fluid intake?

5. Now thinking about any changes you experienced over the clinical trial, can you tell me how the treatment you received during the clinical trial has affected your nocturia, if at all?

- a. Did your nocturia get better compared to before the trial?
 - When did you notice this getting better? At what point during the trial?
 - How much better did your nocturia get?
 - What did this mean for you?
 - Were you able to do things you weren't able to do before? What things? How?
 - How did this make you feel?
- b. Did your nocturia seem to get worse compared to before the trial?
 - When did you notice this getting worse? At what point during the trial?
 - What did this mean for you?
 - How much worse did your nocturia get?
 - Did it stop you from being able to do things in any way? What things? How?
 - How did this make you feel?
- c. Did your nocturia stay the same/not change?
 - What did this mean for you?
 - How did this make you feel?

6. Thinking about just the ways in which your nocturia got better since starting treatment, can you tell me a little more about how this improvement(s) impacted your life?

[Encourage the subject to spontaneously mention the different ways the improvement in their nocturia has impacted them since the trial. If any of the areas below are not mentioned, then probe specifically on these].

- a. More sleep?
- b. Less problems with falling back to sleep?
- c. Feeling less tired?
- d. Greater ability to concentrate?
- e. More productive at work?
- f. Less impact on daily activities?
- g. Less avoidance of activities that you enjoy?
- h. Improved mood?
- i. Less worry about tripping or falling?
- j. Less worry about finding a toilet when away from home?
- k. Less worry about waking others up in the house?
- l. Less worry about worsening of symptoms?
- m. Less need to limit fluid intake?

Were there other positive impacts from taking treatment as part of the clinical trial that we haven't discussed? Tell me about those.

7. [Only ask this if they mentioned worsening in Q5b] **Thinking about just the ways in which your nocturia got worse since starting treatment, can you tell me a little more about how it has impacted your life?**

[Encourage the subject to spontaneously mention the different ways the improvement in their nocturia has impacted them since the trial. If any of the areas below are not mentioned, then probe specifically on these].

- a. Less sleep?
- b. More problems with falling back to sleep?
- c. Feeling more tired?
- d. Less ability to concentrate?
- e. Less productive at work?
- f. More impact on daily activities?
- g. More avoidance of activities that you enjoy?
- h. Impaired mood?
- i. More worry about tripping or falling?
- j. More worry about finding a toilet when away from home?
- k. Less worry about waking others up in the house?
- l. Less worry about worsening of symptoms?
- m. Less need to limit fluid intake?

Were there any other negative impacts from taking treatment as part of the clinical trial that we haven't discussed? Tell me about those.

Part 2: Discussion about the NI Diary and meaningful change (25 minutes)

Introduction by interviewer: *Okay, so now I'm going to ask you to look at the short diary questionnaire – the Nocturia Impact Diary - you will probably recognize it as you completed it as part of the clinical trial. I'm going to ask you how you might respond to the diary questions based on whether or not your nocturia has changed in any way and what those different scores reflect in terms of your actual experiences.*

Please look at the Nocturia Impact Diary which we have sent you a copy of. Do you have it there?

As you may recall, you completed this diary for the 3 days before each clinical trial site visit. The diary asked you about some of the most common ways that nocturia may impact a person in their day-to-day life. The diary contains 11 questions and one additional global, overall, impact question. Each of the items is scored from 0 to 4 where 0=not at all, 1=slightly, 2=moderately, 3=quite a bit, 4=a great deal. So a higher score is worse because it reflects greater impact. The first 11 questions are added up to make a total score, so this score can range from 0 to 44.

8. Looking at the diary and the different aspects of life that are affected by nocturia, can you rank order the 11 areas listed in the diary, from most important to least important?

- a. Taking the first 3 items, ask: What is it about those 3 that make them the most important?
- b. Taking the last 3 items, ask: What makes these the least important?
- c. Are there impacts listed that MUST improve? *INSTRUCTION TO INTERVIEWER: MAKE A NOTE OF HOW MANY IMPACTS THE SUBJECT STATES 'MUST IMPROVE' FOR USE IN Q11 below*
- d. Are there impacts that are not so important to you?

9. Thinking about [impact ranked as #1]:

- a. What does 'not at all' mean to you?
 - Now what does 'slightly' mean to you?
 - 'moderately'?
 - 'quite a bit'?
 - 'a great deal'?
- b. If you experienced a 1-point reduction (eg, from 'moderately' to 'slightly', or a 'great deal' to 'quite a bit') what would that mean to you?
- c. Would a 1-point change across the categories mean the same?
- d. Is a 1-point reduction in [impact ranked as #1] meaningful to you in terms of how you would feel or what you could do?
- e. If no, how many points would you want to reduce [impact ranked as #1] by for it to be meaningful to you?
 - How would you feel or what could you do if you experienced this level of reduction?

10. Repeat Q9 for the impacts stated as 'must improve' in Q8c

INSTRUCTION TO INTERVIEWER: MAKE A NOTE OF HOW MANY POINTS THE SUBJECT WOULD LIKE TO SEE CHANGE ON EACH 'MUST IMPROVE' IMPACT (PROBES D AND E ABOVE). ADD TOGETHER ALL OF THE RESPONSES TO PROBES D OR E AND USE IN Q11.

- 11.** You want to see improvement on [number of impacts mentioned in Q8c] things, and you stated a [THE RANGE OF POINT CHANGES] would be meaningful on each. So, would a [TOTAL OF RESPONSE TO PROBES D AND E ABOVE] change be meaningful?

Part 3: Discussion about nocturnal frequency and meaningful change (10 minutes)

Introduction by interviewer: *Okay, so now I'm going to ask you to discuss how often you get up at night to urinate and what sort of change in frequency would be important for you.*

As you may recall, you completed a diary for 3 days before each clinical trial site visit to report how many times you got up at night to urinate. The average number of times you went to the bathroom at night over these 3 days was then worked out (eg, if you had three events the first night, two the 2nd night and one the 3rd night, your average times of going to the bathroom at night to urinate would be two times).

12. As we just discussed, before the clinical trial you got up at night to urinate X times per night on average (see response to Q3c) and at the end of the clinical trial it was X times per night on average (see response to 1c). This means you had a X unit reduction/increase/same.

Instruction to interviewer: Check that score change is the same as what was discussed during Q5. If there is a reduction go to Q12a–d. If there is not a reduction go to Part 4.

- a. What does it mean for you to go to the bathroom at night, on average, X times less now than before the trial?
- b. Is this an important change for you?
- c. How do you feel because you go to the bathroom at night X times less now?
- d. What are you able to do because of this change in how often you go the bathroom at night?

Instruction to interviewer: if the change is more than one event, ask about the meaningfulness in one unit reduction and repeat questions a and b above; for example, if the subject had a score change of three, ask them:

- *Would two less events be meaningful? Why, why not?*
- *How would you feel or what could you do if you had two less events per night?*
- *How about one less event, would that still be meaningful? Why, why not?*
- *How would you feel or what could you do if you had one less event per night?*

Part 4: Rating of change on the patient global assessment of change and patient global impression of severity (5 minutes).

Introduction by interviewer: *So in this final section, I'd like to get your responses to a few other questions that ask you about your overall impression of how your nocturia has been and how it may have changed. I will read the questions and response options to you and ask that you select the response that best reflects your experience.*

13. Overall, how satisfied are you with how the study medication relieved your nocturia?

- a. Choose from: "Very satisfied," "Satisfied," "Somewhat satisfied," "Neither satisfied nor dissatisfied," "Dissatisfied," "Somewhat dissatisfied," or "Very dissatisfied"
- b. Why did you select that response?
- c. What were you thinking about to make you select X?

14. Thinking back over the course of the clinical trial, would you say your overall health status was?

- a. Choose from: "Very much improved," "Much improved," "Minimally improved," "No change," "Minimally worse," "Much worse," or "Very much worse"
- b. Why did you select that response?
- c. What were you thinking about to make you select X?

15. Check the one number that best describes how your night time urination is now (based on the past 24 hours) (PGI-S)

- a. None
- b. Mild
- c. Moderate
- d. Severe

16. Check the one number that best describes how your night time urination is now, compared with how it was before you began taking medication in this study. (PGI-I Revised)

- a. Very much better
- b. Much better
- c. A little better
- d. No change
- e. A little worse
- f. Much worse
- g. Very much worse

That is the end of the interview today. Do you have any final questions? Thank you so much for taking part today and spending time with me in answering these questions.

Appendix 2

Statistical Design and Operating Characteristics

Trial Code: 000233

**Randomized Dose-Response Trial Investigating 6 Different Oral Doses of
FE 201836 for the Treatment of Nocturia due to Nocturnal Polyuria in Adults**

*Prepared for Ferring
By Berry Consultants, LLC
December 16, 2016*

1 Introduction

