4.2 Sample Size Requirement and Cluster Sampling Design

The primary goal of the exit interview is to estimate meaningful change thresholds for the NI diary within this randomized subject population from the Phase 2 proof-of-concept trial (1:1:1:1:1 ratio; FE201836 versus desmopressin versus placebo). For each treatment arm, subjects who demonstrate improvement in the NI Diary scores from Baseline to End of Treatment will be evaluated using a paired-sample t-test. This sample size calculation is based on NI diary parameters and is a mixed methods design (eg, qualitative and quantitative evidence) in which the equivalence of paired means is tested with significance (alpha) set at 0.05, a correlation of 0.40 between assessments, a combined standard deviation of 10 (95% confidence interval [CI] lower bound equal to 10 and upper bound equal to 15), and minimal difference thresholds estimated from previous research of 8.28 and 10.30 point improvement (based on the 0 – 100 transformation). See [Table 1](#) for further details.

Table 1. Sample Size Requirement for Paired t-test of Mean Difference

Mean Improvement Level on the NI Diary Total	Standard Deviation	Actual Power	Sample Requirement per Treatment Arm	Total Subjects
8.28	10	0.807	16 subjects	96 subjects
10.30	10	0.802	11 subjects	66 subjects

Abbreviations: NI = Nocturia Impact

The above power calculation defines the size of the initial set of exit interviews and the *minimum number of subjects* who will be exit interviewed. On the basis of this sample, the change threshold is estimated for defining meaningful change. Next, the robustness of the threshold estimate to increases in sample size using the steps described below is tested). Based on the results, it will be decided whether or not to conduct additional interviews. A “robust” threshold estimate is defined as one that varies < 1 with the addition of the results of additional interviews.

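### The exit interview asks about one summed NI Diary total and never about a smaller one, so a yes shows a sufficient change but does not locate the subject's threshold

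*Protocol*

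**What the plan says.** The relevant text is the Discussion Guide in Appendix D of the Exit Interview Protocol, which is Appendix 1 of the protocol.

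- Q8c asks "Are there impacts listed that MUST improve", with no limit on how many of the 11 items may be named.
- Q9 takes the top-ranked item and asks "Is a 1-point reduction in [impact ranked as #1] meaningful to you in terms of how you would feel or what you could do". If one point is not enough, it goes on: "If no, how many points would you want to reduce [impact ranked as #1] by for it to be meaningful to you".
- Q10 extends this to the other items: "Repeat Q9 for the impacts stated as 'must improve' in Q8c".
- The interviewer notes the points for each such item and is told: "ADD TOGETHER ALL OF THE RESPONSES TO PROBES D OR E AND USE IN Q11".
- Q11 puts the result to the subject once: "So, would a [TOTAL OF RESPONSE TO PROBES D AND E ABOVE] change be meaningful". Part 2 ends there.

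Part 3 of the same guide treats nocturnal voids differently. Where a subject's reduction exceeds one void, the interviewer goes down one unit at a time, ending with "How about one less event, would that still be meaningful".

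Section 4.2 of the Exit Interview Protocol makes estimation of NI Diary meaningful-change thresholds the primary goal. It sizes the sample on "minimal difference thresholds estimated from previous research of 8.28 and 10.30 point improvement". Section 5.3.1 says thresholds are expressed in raw points and later converted to the 0-100 scale.

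**The concern.** A threshold is the point at which change starts to matter. To find it, one must see where the subject's answer changes. Q11 offers a single total, built by adding answers that were each given for one item alone. If the subject agrees, the interview has shown that improving on all the named items together is enough. It has not shown that less would fall short. If the subject disagrees, the script moves on without asking what would suffice.

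The total also grows with the number of items named, even when the item-level answers are identical. A subject who names many concerns gets a high total whether or not a smaller overall improvement would have satisfied them.

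The introduction to the Exit Interview Protocol says that the regulator asked for these interviews and that the sponsor wants the NI Diary as a co-primary endpoint in registrational studies. Smaller totals that were never asked about cannot be recovered once the interviews are over. The saturation rule in Section 4.2.1 does not help here: more interviews can stabilise an average of sums, but they cannot turn a sufficient change into a smallest one.

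**Working it through.** **The plan's own figures.** Table 1 of Section 4.2 gives power 0.807 with 16 subjects per arm for 8.28 points, and 0.802 with 11 per arm for 10.30 points. Inputs from that section: SD 10, correlation 0.40, alpha 0.05 (taken as two-sided, since sidedness is not stated).

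- SD of the paired difference = 10 × √(2 × (1 − 0.40)) = 10.95.
- Noncentral t, n = 16, difference 8.28: power 0.8066.
- Noncentral t, n = 11, difference 10.30: power 0.8021.
- Six arms: 16 × 6 = 96 and 11 × 6 = 66.

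The table reproduces. The sample-size calculation is not at issue; the check confirms that 8.28 and 10.30 are differences on the 0-100 scale.

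**Scale.** The Total Score runs from 0 to 44, so one raw point is 100/44 = 2.27. The reference values are 8.28 × 0.44 = 3.64 and 10.30 × 0.44 = 4.53 raw points.

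**The Q11 total.** With k items named and p points on each, the total is k × p raw points, or 100 × k × p / 44.

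| Items named (k) | p = 1 | p = 2 |
|---|---|---|
| 1 | 2.27 | 4.55 |
| 2 | 4.55 | 9.09 |
| 3 | 6.82 | 13.64 |
| 4 | 9.09 | 18.18 |
| 5 | 11.36 | 22.73 |
| 11 | 25.0 | 50.0 |

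At one point per item, the lowest answer Q9 can yield, the total varies 11-fold with k alone. One to three items stay below both reference values, four pass 8.28 and five pass 10.30. The documents give no distribution for k, so the table shows a range and does not predict where the average will fall. Points per item matter too, as the second column shows.

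**What each answer establishes.** Take a subject who names five items at one point each.

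- Yes at Q11: a total of 5 raw points (11.4) is sufficient. The same subject has already called one point on a single item meaningful. Taken at face value, the threshold lies anywhere from 1 to 5 raw points (2.3 to 11.4), and nothing in the script narrows this.
- No at Q11: the threshold is above 5 raw points, by an unknown amount.

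**The case against.** Several points on the other side have weight.

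- **Must may mean must.** If a subject regards every named item as indispensable, improvement on fewer items would not do. Because Q9 starts at one point and goes up only if needed, the sum is then the smallest total that meets the subject's requirements, and its dependence on the number of items is legitimate. This stands as a condition on the conclusion. The script cannot distinguish such subjects from those for whom less would do.
- **Other evidence feeds the threshold.** Protocol Sections 7.1.1.3.1 and 10.3.1.1 provide for anchor analyses with PGI-I and PGI-S in a separate psychometric plan, and Section 5.3 of the Exit Interview Protocol for triangulation with trial results. This limits the consequence. It does not repair Q11, the only question in the guide that puts a Total Score change to the subject.
- **Interviewers may probe.** The notes to interviewers allow general probing, so a no need not pass in silence. But unscripted probes will not give a comparable number for every subject.
- **Voids are easier.** Stepping down from a small, experienced count is more natural than stepping down a 44-point composite by telephone. That is fair, and it bears on how the added probe is worded.

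Two stronger readings may tempt a reader. The first is that the top-ranked item is added twice, once from Q9 and again from Q10. The instruction before Q11 has the interviewer note the points for each must-improve impact, which gives one value per impact. The second is that the mean, SD and 95% CI in Section 4.2.1 would merely describe item counts. No section says that those statistics come from Q11 alone, and the total also reflects points per item.

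**Conclusion.** The point holds in a limited form. Q11 bounds each subject's threshold from one side only: from above after a yes, unless the named items are all non-negotiable, and from below after a no. With identical 1-point answers the recorded total runs from 2.3 to 25.0 on the 0-100 scale according to the number of items named, so it depends strongly on that number.

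Whether the resulting threshold would exceed 8.28 or 10.30 cannot be determined, because the number of items subjects will name is not given. A reader might infer that the threshold will certainly be too high; the documents do not support this. Nor does the issue touch this trial's own endpoints: the responder endpoints in SAP Section 2.2 are based on voids. The value at risk is the interview's contribution to interpreting the NI Diary, which that study names as its primary goal. This is a cheap improvement worth making, not a defect in the trial's efficacy analysis.

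**What to change.** Keep Q11 and record its answer as now. Then add a scripted follow-up:

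- After a yes, ask whether a smaller total would still be meaningful, and continue until the subject says no. The smaller total can be put as improvement on fewer of the named items (for example, dropping the lowest-ranked first, using the order from Q8) or as the total reduced in steps.
- After a no, step up until the subject says yes.
- Record the smallest accepted total as the subject's threshold, alongside the original sum, so that both can be reported.

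The step-down uses a technique already in Part 3 of the guide. The cost is a few more minutes in the 25-minute Part 2 and some abstract questions by telephone; framing the steps as fewer items may ease the latter. The guide's timings already add to its one-hour limit (5 + 15 + 25 + 10 + 5 = 60 minutes), so the extra minutes need to be found within it or the limit relaxed slightly.
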